**RANDOMIZED PHASE III, DOUBLE BLIND, PLACEBO CONTROLLED STUDY OF
PROPHYLACTIC GABAPENTIN FOR THE REDUCTION OF RADIATION THERAPY
INDUCED PAIN DURING THE TREATMENT OF OROPHARYNGEAL SQUAMOUS
CELL CARCINOMA**

NCT Number: 03269344

2/6/2017

**RANDOMIZED PHASE III, DOUBLE BLIND, PLACEBO CONTROLLED STUDY OF
PROPHYLACTIC GABAPENTIN FOR THE REDUCTION OF RADIATION THERAPY
INDUCED PAIN DURING THE TREATMENT OF OROPHARYNGEAL SQUAMOUS
CELL CARCINOMA**

Study Team

Principal Investigator

[name] MD
Department of Radiation Oncology

Scientific Advisors

[name] MD PhD
[name] MD
Department of Radiation Oncology

[name] MD
Department of Hematology/ Oncology

Biostatistics

[name] MA
[name] PhD
Department of Public Health Science

Research Pharmacy

[name] Pharm D
[name] BS Pharm
Research Pharmacy

Participating Sites

Henry Ford Hospital
[name]
[name]

Protocol Version 1.0 1/6/2017

Randomized Phase III, Double-Blind, Placebo Controlled Study of Prophylactic Gabapentin for the Reduction of Radiation Therapy Induced Pain During the Treatment of Oropharyngeal Squamous Cell Carcinoma

SCHEMA

Pre-study: Determine eligibility

Signed Informed consent

| | | | |
|----------|-------------------------|----------|--|
| S | | R | Arm 1: (control): Standard supportive care during |
| T | | A | definitive treatment plus placebo |
| R | | N | |
| A | Smoking History: | D | Arm 2: 600 mg of gabapentin TID (1800 mg daily |
| T | Current smoker | O | total) during definitive treatment |
| I | Ex-smoker or non-smoker | M | Plus standard supportive care |
| F | | I | |
| Y | | Z | |
| | | E | |

Patient population: Patients being treated with radiation and concurrent chemotherapy for Stage III and IV (non-metastatic) squamous cell carcinoma of the oropharynx

Required Sample Size: 60

| | Page |
|--|------|
| SCHEMA..... | 2 |
| 1. INTRODUCTION | 4 |
| 2. PATIENT SELECTION | 6 |
| 3. REGISTRATION PROCEDURES | 7 |
| 4. TREATMENT PLAN | 7 |
| 5. DOSING DELAYS/DOSE MODIFICATIONS | 13 |
| 6. ADVERSE EVENT REPORTING | 13 |
| 7. PHARMACEUTICAL INFORMATION | 14 |
| 8 STUDY CALENDAR | 14 |
| 9. STATISTICAL CONSIDERATIONS..... | 15 |
| REFERENCES | 18 |
| APPENDIX..... | 19 |

1.1 INTRODUCTION

1.1.1 Specific Aims

Strategies to minimize and mitigate external beam radiation therapy related mucositis and pain during the treatment of head and neck cancer remain limited. We hypothesize that gabapentin could be used to delay or reduce treatment-related pain, reliance on opioid medication, and improve the quality of life for these patients. The specific aims of this proposed study include the following:

- Evaluate the reduction or delay of mucositis related pain and morbidity with the use of gabapentin in patients with stage III or IV oropharyngeal squamous cell carcinoma undergoing definitive radiation with concurrent chemotherapy as part of their cancer management, compared to standard supportive side effect mitigation – using patient reported quality of life endpoints such as the Patient-Reported Oral Mucositis Symptoms (PROMS) scale.
- Assess morphine-equivalent opioid use in both treatment arms by collecting the patient's narcotic use in the previous 24-hour period at each weekly evaluation during radiation treatment.
- Report on change in Speech and swallow performance, as measured by the Performance Status Scale (PSS) for Head and Neck Cancer Patients.
- Evaluate changes in weight from baseline throughout treatment between the two arms.
- Calculate the proportion of patients who end up requiring a feeding tube by the end of treatment in both arms.
- Evaluate changes in patient-report quality of life using the Functional Assessment of Cancer Therapy Head & Neck (FACT-HN) and PRO-CTCAE metrics.
- Evaluate the adverse events associated with gabapentin.
- Evaluate the severity of radiation mucositis (grade 3-4, CTCAE, v. 4).

1.2 Background and Significance

1.2.1 Head and Neck Cancer/ Treatment Related Morbidity

There are an estimated 55,070 patients with head and neck cancer in the United States, with an estimated 12,000 deaths annually and a rising incidence of Human Papilloma Virus-related oropharyngeal cancer. [1, 2] Unfortunately, a large portion of these patients present with locally advanced disease. [3] Definitive radiation with concurrent platinum-based chemotherapy is the primary treatment for stage III and IV oropharyngeal carcinoma.

Chemotherapy has been evaluated in multiple trials in conjunction with radiation therapy to treat a variety of head and neck cancers. A comprehensive meta-analysis revealed an overall survival

benefit of 7% at 2 years and 8% at 5 years with the concurrent use of cisplatin-based chemotherapy. [4] This, however, has not come without major treatment related toxicity and morbidity. The addition of chemotherapy to radiation has been shown to potentially increase short-term toxicity burden by 300% (increased relative risk). [5]

Strategies to minimize and mitigate treatment related mucositis and pain remain limited. Most practitioners utilize a combination of oral anesthetic mouthwashes, opioid medication, infection control, and lifestyle modification. [6]

1.2.2 Gabapentin

Gabapentin is an anticonvulsant and has been used to manage neuropathic pain and is FDA-approved for the treatment of post-herpetic neuralgia and partial onset seizures. While opioids are effective in treating nociceptive pain, head and neck patients experience both neuropathic (burning, aching, stabbing) and nociceptive (dull, sore, tender) pain. [7] Opioid medications have adverse effects including constipation, nausea, vomiting, sedation, impaired psychomotor function, urinary retention, hyperalgesia, as well as the potential for dependence. [8] Gabapentin is thought to provide neuropathic relief of pain by inhibition of alpha-2-delta-1 receptor upregulation in the dorsal horn, reversing pain mediated regulators of pain. [9] It is generally well tolerated, although common adverse effects include somnolence, dizziness, peripheral edema, and fatigue. [10]

Gabapentin has evolved as a strategy to reduce morbidity in patients undergoing radiation treatment. Bar-Ad et al. retrospectively evaluated their experience using gabapentin and found less opioid use and less treatment breaks when using this strategy for patients undergoing chemoradiation treatment to the head and neck. Similar findings were reported for patients undergoing post-operative radiation therapy without chemotherapy. [11] Similarly, Starmer et al retrospectively analyzed 23 patients with oropharyngeal SCC treated with chemoradiation and found that patients used their PEG tubes later, had their PEG tubes removed earlier, and reported less pain and duration of pain in those that used gabapentin. [1] Lastly, Yang et al in their retrospective analysis of their head and neck database found gabapentin use to be associated with reduced PEG tube dependence. [12]

All of these reports are small, single institution, retrospective experiences and are subject to patient selection biases. Given the advantages of gabapentin use during chemoradiation in reducing treatment related pain and PEG tube dependence, we seek to prospectively evaluate this drug in a randomized, blinded setting. This will validate these findings with a greater level of evidence.

1.2.3 Summary and Rationale for This Study:

Given the lack of effective strategies to mitigate treatment related pain from mucositis during head and neck cancer treatment as well as lack of randomized, prospectively evaluated evidence

supporting gabapentin use in this setting, we hereby propose this randomized clinical trial to evaluate the effectiveness of gabapentin in delaying or reducing treatment-related pain, reliance on opioid medication, and improving the quality of life for these patients.

2. PATIENT SELECTION

2.1 Conditions for Patient Eligibility:

- 2.1.1 Patients being treated with combination radiation and chemotherapy (definitive) therapy for locally advanced (Stage III and IV) squamous cell carcinoma of the oropharynx.
- 2.1.2 Age ≥ 18 .
- 2.1.3 ECOG performance status 0-1.
- 2.1.4 Patients must provide study specific informed consent prior to study entry and be able to fill out toxicity and quality of life related questionnaires.
- 2.1.5 Patients should be concurrently treated with any of the following chemotherapy regimens: high-dose every three week cisplatin, low dose weekly cisplatin, or weekly carboplatin.

2.2 Conditions for Patient Ineligibility:

- 2.2.1 Patients may not be receiving gabapentin, any other investigational agents, or other anticonvulsants.
- 2.2.2 Patients with metastatic disease are excluded from this clinical trial.
- 2.2.3 Patient with allergies or hypersensitivity to gabapentin.
- 2.2.4 Patients receiving surgery as part of their definitive management.
- 2.2.5 Patients who have received prior chemotherapy or radiation therapy for head and neck cancer.
- 2.2.6 Patients unable to complete the required forms; however, verbal completion is adequate if recorded on the form daily.
- 2.2.7 Uncontrolled serious illness including, but not limited to, ongoing or serious active infection requiring IV antibiotics for over 30 days, symptomatic congestive heart failure, unstable angina pectoris, cardiac arrhythmia other than chronic, stable atrial fibrillation, immunocompromised state, significant hepatic insufficiency, significant hematological disease, and any serious or unstable psychological condition.
- 2.2.8 Patients on any of the following medication that cannot find a suitable substitute during the study period: azelastine, orphenadrine, paraldehyde, thalidomide.
- 2.2.9 Patients with severe renal insufficiency (creatinine clearance of < 60 ml/minute)

2.3 Required laboratory data (to be done at time of enrollement):

2.3.1 Creatinine

2.4 Inclusion of Women and Minorities: Both men and women and members of all races and ethnic groups are eligible for this trial.

3. REGISTRATION PROCEDURES

Patient registration can occur only after evaluation for eligibility is complete, eligibility criteria have been met, and the study site has Institutional Review Board approval. Patients must have signed and dated all applicable consents and authorization forms. To register a patient to this study, the signed and dated eligibility checklist, along with any necessary supporting documentation, and the signed patient consent form will be forwarded to the responsible data manager. To complete the registration process, the data manager will assign a patient study number, in sequential order of consent, register the patient to the study, and contact the treating investigator and responsible research nurse to confirm registration.

4. TREATMENT PLAN

4.1 Chemotherapeutic Agent Administration

Chemotherapy, delivered concurrently with radiation therapy, will ultimately be determined by the treating medical oncologist. Patients receiving any of the following regimens will be eligible:

High-dose cisplatin - Cisplatin: 100 mg/m²/day, every 3 weeks during radiation treatment, for a maximum of 3 doses.

Carboplatin - Carboplatin: Target area under curve (AUC) 2 once weekly for a maximum of 6 doses.

Weekly cisplatin - Cisplatin: 40 mg/m²/day, weekly during radiation treatment for a maximum of 6 doses.

4.2 Radiation Therapy

Radiation therapy, delivered concurrently with chemotherapy, will ultimately be determined by the treating radiation oncologist. The following guidelines should be followed:

4.2.1 Dose specifications:

Volumes and Lymph node levels should be defined as per the RTOG Head and Neck atlas <http://www.rtog.org/CoreLab/ContouringAtlases/HN.aspx>.

Definitive treatment (all primary treatment should be delivered with concurrent chemotherapy as per the treating medical oncologist) will be done with simultaneous integrated dosing (SID) in 35 fractions to a total dose of 70 Gy, 63 Gy and 56 Gy to the high-risk, intermediate-risk and low-risk CTVs, respectively.

4.2.2 Physical Factors:

All subjects will undergo radiographic imaging required for radiation treatment planning purposes using a CT scanner. Digitally reconstructed radiographs from the CT will simulate the patient geometry during radiation treatment, including the localization and immobilization methods. A virtual treatment planning procedure is used to design treatment fields mathematically from the CT images.

4.2.3 Target Volumes

The GTV will be treated as the PTV70 (CTV 70+margin) will receive 70 Gy in 35 fractions (2 Gy per fraction)

Creation of the PTV70 is as follows: GTV70 defined from CT-sim and diagnostic CT fusion. GTV-p (primary tumor) and GTV-n (positive lymph nodes) are to be delineated.

CTV70-p=GTV-p with 1 cm expansion, except when the GTV-p is at the base of tongue, then the CTV70-p will be the GTVp with a 1.5 cm expansion.

CTV70-n will be created using the GTV-n with a 1 cm expansion.

CTV70 will then be defined using the CTV70p+ CTV70n. The CTV70 should be modified so as not to cross fascial plains or vertebral bodies.

PTV70 will be defined as the CTV70 with a 0.5 cm expansion. PTV70 should be modified to be cropped 3 mm from the skin surface.

High risk PTV63 (CTV63+margin) areas will receive 63 Gy in 35 fractions (1.8 Gy per fraction)

The CTV63 delineated to include the involved lymph node level, and any adjacent lymph node levels. For example for a right sided level 2 lymph node, CTV63 will include right sided level-2, level-3, level-5, and level-1b. Level-2 should be defined to the base of skull on the involved side (sacrificing parotid on involved side).

PTV63 will be defined as CTV63 with a 0.5 cm expansion.

Low risk PTV56 (CTV56+ margin) regions will receive 56 Gy in 35 fractions (1.6 Gy per fraction)

The CTV56 will include the uninvolved neck, if clinically indicated to be treated. Level-2 in the uninvolved neck should be treated to the level of C1, allowing for parotid sparing. Also included

in the CTV56 is any lymph node level on the involved side that is not included in the CTV63, and is still at low risk of tumor involvement. Such that if right side level-2 LN is involved, then right sided level-4 would be defined as CTV 56. Right sided Level-1a would be included only if clinically indicated.

PTV56 will be defined as CTV56 with a 0.5 cm expansion.

4.2.4 Field Arrangement:

IMRT will be used to cover the primary or planning target volume (PTV), provided that the normal tissue constraints described below are met.

4.2.5 Beam Shaping:

A multileaf collimation system will be used to comply with field margin and normal tissue dose requirements.

4.2.6 Treatment Equipment:

Treatment will be administered on an isocentrically mounted megavoltage linear accelerator with photon energy ≥ 6 MV. Typically, the source-to-axis distance (SAD) will be 100 cm. IMRT will be delivered using volumetric modulated arc therapy (VMAT) technique.

4.2.7 Beam Verification:

Standard IMRT QA procedures developed at our institution will be performed, including monitor units verification, intensity map verification, as well as point dose measurements. Cone beam CT scans will be obtained daily prior to radiation delivery to ensure proper patient positioning.

4.2.8 Dosimetry:

The uniformity requirement will be $\pm 5\%$ of the total dose at the prescription point within the planning target volume.

4.2.9 Critical Normal Structures:

QUANTEC Dose Constraint Parameters will be used. Modifications to allow for adequate tumor coverage are allowed at the discretion of the treating physician.

4.2.10 Radiation Therapy Adverse Events and Treatment Modifications

Grade 3-4 (CTCAE, v. 4) therapy-induced mucositis and/or dysphagia, which are enhanced by cisplatin, are expected to develop in about two thirds of patients. Nutritional evaluation prior to the initiation of therapy is highly recommended. Placement of a feeding tube should be recorded, as should use of a feeding tube during and after treatment. Other common radiation adverse

events include: fatigue, weight loss, regional alopecia, xerostomia, hoarseness, transient ear discomfort, dysgeusia, and skin erythema and desquamation within the treatment fields.

Less common long-term treatment adverse events include: hypothyroidism, loss of hearing, chronic swallowing dysfunction requiring permanent feeding tube, and cervical fibrosis. Much less common radiation adverse events include: mandibular osteoradionecrosis (< 5% incidence with attention to the dental recommendations), and cervical myelopathy (< 1% with restriction of spinal cord dose to ≤ 45 Gy).

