4.5 Assignment of interventions

4.5.1 Allocation sequence generation

Separate randomization lists will be produced by a statistician for current smokers as well as for former/ non-smokers with a goal of 1:1 allocation to both treatment arms.

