9. STATISTICAL CONSIDERATIONS

9.1 Study Endpoints/ Analysis Plan

9.1.1 Primary endpoint

The primary endpoint is change in quality of life and pain, as measured by the Patient-Reported Oral Mucositis Symptoms (PROMS) scale over the entire study period. This will be measured at baseline and weekly during clinic visits. Additional measurements will be obtained at 6-weeks (first follow-up) from the time of radiation treatment completion.

The PROMS scale consists of 10 questions on a visual analogue scale of 100-mm lines addressing oral functions affected by oral mucositis.[13] This questionnaire has been validated in patients undergoing radiation treatment for head and neck cancers and correlates well with clinician determined scores of mucositis.[14]

Repeated measures analysis of variance (ANOVA) will be used to determine if there was a significant difference between the mean PROMS scores of the two groups over the entire study period, and t-tests will be used to examine if there was a difference in the PROMS scores for the two groups at each week of the study period.

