9.1.2 Sample size/ Justification of Number of Subjects

Based on reported means and standard deviation of PROMS scores of patients undergoing radiation treatment, a total of 60 patients will be required to evaluate a 16% reduction in PROMS score at week 7 (final week) of radiation treatment, with $\alpha = 0.05$ and power = 80%. This assumes a 10% dropout rate.

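### Planned chemotherapy regimen is not a prespecified covariate in the PROMS analysis, although the protocol says cisplatin enhances mucositis and both cisplatin and carboplatin are allowed; a modest, optional gain in precision

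*Combined protocol and SAP*

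**What the plan says.** Section 4.2.10, on radiation adverse events, refers to grade 3-4 "therapy-induced mucositis and/or dysphagia, which are enhanced by cisplatin" and expects these in roughly two thirds of patients. It gives no rate by regimen and names no comparator.

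Section 2.1.5 allows "high-dose every three week cisplatin, low dose weekly cisplatin, or weekly carboplatin". Section 4.1 leaves the choice to the treating medical oncologist.

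Smoking status is the only balancing factor (section 4.5.1): "Separate randomization lists will be produced by a statistician for current smokers as well as for former/ non-smokers".

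The primary analysis (section 9.1.1) is a comparison of two groups: "Repeated measures analysis of variance (ANOVA) will be used to determine if there was a significant difference between the mean PROMS scores". Weekly t-tests are added, and no covariate is named. The same section says that PROMS agrees well with clinicians' mucositis scores. Grade 3-4 mucositis is compared by Fisher's exact test (section 9.2.5). The only model with covariates is the one for opioid use (section 9.2.4). It lists stratification, arm and compliance as a minimum set and does not name regimen.

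**The concern.** The protocol names a factor that raises the toxicity under study, enrols patients who will differ on that factor, and then uses it in no planned analysis. If regimen does predict PROMS, two things follow. Variation between regimens stays in the error term and costs some power. And with about 30 patients per arm, the carboplatin share can differ between arms by chance, so one realised estimate may sit slightly away from where an adjusted one would. Adjusting only after an imbalance has been seen is open to challenge, whereas a covariate named in advance is not.

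**Working it through.** **1. The plan's own figure.** Section 9.1.2 states that "a total of 60 patients will be required to evaluate a 16% reduction in PROMS score at week 7 (final week) of radiation treatment". The stated settings are alpha 0.05, 80% power and 10% dropout. No mean or SD is given, so 60 can only be solved backwards. Sidedness is not stated; two-sided is assumed.

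- Evaluable patients: 60 × 0.9 = 54, or 27 per arm.
- Standard error of a difference in SD units: √(2/27) = 0.272.
- Detectable difference: (1.960 + 0.842) × 0.272 = 0.762 SD (0.777 SD with the t distribution).
- If 16% is relative to the control mean, the implied SD/mean is 0.16/0.762 = 0.21.

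The figure of 60 is therefore attainable for some SD but cannot be confirmed. The steps below take 80% power at 0.762 SD as the starting point. They treat PROMS as a single week-7 comparison, as the sizing does.

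**2. Power gained by adjusting.** Two inputs are assumed because the documents give neither: the carboplatin share p (5-50%) and the cisplatin-carboplatin difference e in PROMS (0-0.8 SD).

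- Variance explained by regimen: R² = p(1 − p)e².
- Adjusted power: Φ(0.762 / (0.272 × √(1 − R²)) − 1.960).
- Upper corner, p = 0.5 and e = 0.8: R² = 0.25 × 0.64 = 0.16. Then 0.762/√0.84 = 0.832, and 0.832/0.272 − 1.960 = 1.10, giving power of 86.4%.
- Rare carboplatin, p = 0.05 and e = 0.8: R² = 0.0475 × 0.64 = 0.030, giving power of 81.2%.

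| Carboplatin share | e = 0 | e = 0.1 | e = 0.3 | e = 0.5 | e = 0.8 |
|---|---|---|---|---|---|
| 5% | 80.0% | 80.0% | 80.2% | 80.5% | 81.2% |
| 10% | 80.0% | 80.0% | 80.3% | 80.9% | 82.3% |
| 20% | 80.0% | 80.1% | 80.6% | 81.6% | 84.1% |
| 30% | 80.0% | 80.1% | 80.7% | 82.1% | 85.3% |
| 50% | 80.0% | 80.1% | 80.9% | 82.5% | 86.4% |

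The formula is slightly generous. It ignores the chance correlation between regimen and arm, which costs about 1/(54 − 1) = 2% of variance on average. Where R² is below about 0.02, the net effect is nil or marginally negative.

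**3. Simulation at 27 per arm (8,000 runs per setting, true difference 0.762 SD).**

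| p, e | Unadjusted power | Adjusted power |
|---|---|---|
| 0.2, 0.5 | 78.4% | 78.6% |
| 0.3, 0.8 | 78.5% | 83.4% |
| 0.5, 0.8 | 78.9% | 84.4% |

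With no treatment effect, the unadjusted test rejected in 4.9-5.7% of runs, close to the nominal 5%.

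**4. Chance imbalance.** Hypergeometric split of 60 patients into 30 per arm, ignoring the smoking strata:

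| Carboplatin patients | Gap of at least 10 points | Gap of at least 20 points |
|---|---|---|
| 3 (5%) | 24% | impossible |
| 6 (10%) | 20% | 2% |
| 12 (20%) | 33% | 10% |
| 18 (30%) | 40% | 16% |
| 30 (50%) | 44% | 20% |

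A 20-point gap moves the PROMS difference by 0.20 × e, which is 0.06 SD at e = 0.3 and 0.16 SD at e = 0.8. That is 8% to 21% of 0.762 SD. Even the larger shift is 0.16/0.272 = 0.59 of a standard error.

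**5. Mucositis.** With an assumed regimen gap of 10-30 points in grade 3-4 events, a 20-point imbalance shifts the arm difference by 2-6 points. The standard error, using the protocol's two-thirds rate, is √(2 × 2/3 × 1/3 / 30) = 12 points.

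**The case against.** The strongest objection is that section 4.2.10 is being asked to carry too much. It says that cisplatin enhances these toxicities but not relative to what. In a section on radiation adverse events, it reads naturally as radiation with cisplatin against radiation alone. All patients in this trial receive a platinum drug. A reader might infer that the protocol itself calls carboplatin less toxic to the mucosa; it does not. The step from mucositis to PROMS is indirect as well. All of this stands, and it is why the gain is given as a range that starts at zero.

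A reader might also infer that the unadjusted analysis is biased or its test invalid. The documents do not support that. Allocation is randomised, the standard error already covers chance imbalance, and the simulated error rate is near 5%.

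Third, covariate adjustment is optional, and choosing this covariate over others is a judgement. That stands too. So does the point that merging the two cisplatin schedules is a choice: the documents do not compare them. Section 4.2.10 names cisplatin without a schedule, so a two-level split follows its wording and costs only one degree of freedom.

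Finally, the documents do not say outright that the regimen is settled before allocation. Section 2.1.5 makes it a condition of eligibility, and section 3 requires the eligibility evaluation to be complete before registration, so the intended regimen should be known by then.

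**Conclusion.** The point holds as a low-priority improvement. The primary analysis leaves out a plausibly prognostic baseline factor that the protocol's own text suggests. Over the assumed ranges, the cost is between nothing and about 6 points of power, plus exposure to a chance shift of up to 0.16 SD under a 20-point imbalance. The top of the range needs a 50% carboplatin share and a regimen effect of 0.8 SD, which is larger than the treatment difference the trial can detect with 80% power. At a 10% share, power rises only to about 80-82%.

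A reader might go further and fault the randomisation for not stratifying by regimen, or the Fisher's exact test for not using it. Neither follows. Stratifying by smoking alone gives a valid 1:1 comparison, a covariate recovers most of the available precision, and the possible shift in the mucositis comparison is small against its standard error.

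**What to change.** - Add a field to the eligibility checklist for planned regimen (cisplatin or carboplatin), completed before allocation.
- Add a sentence to section 9.1.1: the repeated-measures PROMS model will include planned regimen as one fixed between-patient covariate.
- Define the covariate as the regimen planned at randomisation. The regimen received can change because of toxicity, so adjusting for it would condition on something that happens after randomisation.
- Leave the randomisation lists and the Fisher's exact test in section 9.2.5 unchanged. A mucositis comparison stratified by regimen may be reported as supportive only; at a 20% carboplatin share that stratum would hold about 6 patients per arm.

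The cost is one checklist field, one sentence of analysis text and one degree of freedom among about 54 evaluable patients. The gain may be negligible, and if regimen proves unrelated to PROMS there is a very small loss of precision.
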